7.3.4. Strategy for Intercurrent (Post-Randomization) Events

- All Endpoints will use the same strategy for intercurrent events as defined in Section [7.1.4.](#)

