
 For use of rescue medication endpoint, for a subject to be counted in a time period (except for baseline where at least 14 days non-missing entries required) they must have at least one diary entry recorded for that endpoint during that time period. For E-RS endpoint, for a subject to be counted in a time period they must have at least 16 days non-missing diary entries recorded for that endpoint during that time period. Any daily diary data that were collected post-study treatment discontinuation will be excluded from any analyses, including 4-weekly interval data summaries. 		

Calculation of Daily eDiary Endpoints
Use of Rescue Medication via E-diary

 The mean number of inhalations of rescue use per day and percentage of rescue-free days will be calculated during the 4-weekly interval intervals defined above.
EXACT PRO
EXACT Respiratory Symptoms

 The 4-weekly mean scores for E-RS, and the subscales RS-Breathlessness, RS-Cough and Sputum, and RS-Chest Symptoms will be calculated as the mean of the daily scores in the 4-weekly intervals defined above.
EXACT-RS and Subscale Scores Responder

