
For each four weekly period;
 
 A subject will be considered as a responder according to E-RS total score if their 4-weekly mean change from baseline EXACT-RS ≤ -2.0. A subject will be considered as a non-responder according to E-RS total score if their 4-weekly mean change from baseline EXACT-RS >-2.0. A subject will be considered as a responder according to RS-Breathlessness score if their 4-weekly mean change from baseline RS-Breathlessness ≤ -1.0. A subject will be considered as a non-responder according to RS-Breathlessness score if their 4-weekly mean change from baseline RS-Breathlessness >-1.0. A subject will be considered as a responder according to RS-Cough & Sputum score if their 4-weekly mean change from baseline RS-Cough & Sputum ≤ -0.70. A subject will be considered as a non-responder according to RS-Cough & Sputum score if their 4-weekly mean change from baseline RS-Cough & Sputum >-0.70. A subject will be considered as a responder according to RS-Chest Symptoms score if their 4-weekly mean change from baseline RS-Chest Symptoms ≤ -0.70. A subject will be considered as a non-responder according to RS-Chest Symptoms score if their 4-weekly mean change from baseline RS-Chest Symptoms >-0.70. Missing data will be handled as outlined in Section 10.6.2.

Rescue use for EMDI

- Will be analysed over Weeks 1 – 24 only
- The Medication Sensor Observation Period for each subject will be defined by the first date of sensor sync and the last date of sensor sync recorded in the database. Since a recorded rescue inhaler usage event in the database is also considered a sync event, if no first sync date is recorded, the date of the first rescue inhaler usage event will be used as the start date of observation. If no last sync date is recorded, the date of the last rescue inhaler usage event will be used as the end date of observation.
- A rescue occasion is defined as an inhaler usage event(s) in which one or more puffs occur within 2 minutes of each other, starting with the first reported puff.
- Days within the Medication Sensor Observation Period with no recorded rescue inhaler usage by the sensor will be assigned a rescue inhaler usage of 0.

Deterioration

- A Clinically Important Deterioration (CID) will be defined by a composite endpoint. A subject is considered to have deteriorated if, in the period from start of treatment to treatment stop + 1 day, one or more of the following occurs (definition dependent);

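### The exploratory eMDI rescue endpoints have no on-treatment cut-off: the window runs to the last sensor sync, and days without recorded use score 0

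*SAP*

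**What the plan says.** The eMDI rules are in SAP 10.5.3, under rescue use for eMDI.

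- Window: "The Medication Sensor Observation Period for each subject will be defined by the first date of sensor sync and the last date of sensor sync". A recorded use of the inhaler also counts as a sync.
- Fallback: "If no last sync date is recorded, the date of the last rescue inhaler usage event will be used as the end date of observation".
- Outer limit: "Will be analysed over Weeks 1 – 24 only".
- Silent days: "Days within the Medication Sensor Observation Period with no recorded rescue inhaler usage by the sensor will be assigned a rescue inhaler usage of 0".

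None of these rules mentions the study treatment stop date or the return of the inhaler.

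The same section treats eDiary rescue use differently: "Any daily diary data that were collected post-study treatment discontinuation will be excluded from any analyses, including 4-weekly interval data summaries". Section 5.2 sets an eDiary day with a missing puff count to missing, not to zero. The eMDI baseline in 5.2 is tied to dosing: it is built for each combination of sensor and subject, and it closes the day before first dose.

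For the exploratory endpoints, which include both eMDI measures (7.3.1), 7.3.4 states: "All Endpoints will use the same strategy for intercurrent events as defined in Section" 7.1.4. That section targets the effect had every subject remained on the assigned treatment.

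**The concern.** The last sync is a property of the device. If it falls after the subject stopped study drug, the days in between belong to the Weeks 1–24 value as the rule is written, although the declared estimand has no place for them. The analysis model gives no protection. Section 7.3.5.1 drops visit from the eMDI model, so each subject contributes one Weeks 1–24 value with the off-treatment days averaged into it. In the eDiary model the 4-weekly periods after stopping are simply missing and are handled under the missing-at-random assumption.

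A day after final return of the inhaler cannot show use, so a zero there is an artefact. It raises the percentage of rescue-free days and lowers mean daily occurrences. Tables 2.65 and 2.67, and their maintenance-naive repeats 2.121 and 2.123, report analyses of these endpoints.

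**Working it through.** **Which exclusions reach eMDI data.** The exclusion of post-discontinuation data is worded for daily diary data, and the slotting table that leaves out post-treatment records is introduced as covering eDiary records. The eMDI rules sit in a separate block that does not refer to either. A programmer who follows that block applies two limits only: last sync and Weeks 1–24.

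**Plan's own figure.** The SAP gives no figure for the eMDI window or for late syncs, so there is nothing to reproduce. Section 2.3 gives 2424 randomised and about 2181 completing: 1 − 2181/2424 = 10.0% non-completion across the trial.

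**Illustration.** These inputs are assumptions:

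- T = day of treatment stop
- r = rescue-free share up to T
- g = days from stop to last sync, with T + g no more than 168
- s = rescue-free share scored in those g days
- denominator = days inside the observation period

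Apparent rescue-free share = (rT + sg)/(T + g)

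Shift = g(s − r)/(T + g)

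If all g days are scored 0 (s = 1), mean daily use is multiplied by T/(T + g).

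With T = 84, r = 40% and s = 1:

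| g | Apparent rescue-free share | Shift (points) | Mean use multiplied by |
|---|---|---|---|
| 0 | 40.0% | 0 | 1.00 |
| 7 | (33.6 + 7)/91 = 44.6% | 4.6 | 84/91 = 0.92 |
| 28 | (33.6 + 28)/112 = 55.0% | 15.0 | 84/112 = 0.75 |
| 84 | (33.6 + 84)/168 = 70.0% | 30.0 | 84/168 = 0.50 |

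With r from 60% down to 20%, the shift is 3.1 to 6.2 points at g = 7, 10 to 20 at g = 28, and 20 to 40 at g = 84.

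**If the subject still holds the inhaler.** Recorded use then counts as use and s need not be 1. With T = 84, g = 28, r = 40% and s = 20%, the shift is 28 × (−0.20)/112 = −5 points. Before return, the direction is open.

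**Arm level.** Suppose all 10% of non-completers stop at T = 84 with r = 40% and s = 1. The arm mean rises by 0.10 × 4.6 = 0.5, 0.10 × 15 = 1.5 or 0.10 × 30 = 3.0 points for g = 7, 28 or 84.

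**Treatment difference.** With equal stopping and the same pattern in each arm, the bias is 0. If stopping differs by 5 percentage points, it is 0.05 × 4.6 = 0.2, 0.05 × 15 = 0.75 or 0.05 × 30 = 1.5 points.

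**After the fix.** g = 0, and the subject's value returns to r (40.0%).

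**The case against.** The best defence is that the effect may never occur. It needs a sync after treatment stop, and the SAP neither says nor rules out that sensors sync so late. Under the schedule in 10.1.1, withdrawing subjects return promptly for the Early Withdrawal visit, where rescue medication is collected, so long gaps would be unusual. Where no last sync is recorded, the window closes at the last recorded use and no run of zeros can follow it. Days after stopping but before return may be genuine zeros or recorded use. All of this stands, and it limits the size, but it does not supply the missing cut-off. A sync at or after an Early Withdrawal visit held later than the last dose is enough to admit off-treatment days.

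It also stands that the endpoints are exploratory and lie outside the inference scheme of 2.4, that the secondary eDiary rescue endpoints already exclude such data, and that eMDI is used only at some sites. The 10% is trial-wide non-completion and not the share of eMDI subjects with a late sync.

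One could argue that limiting the analysis to Weeks 1–24 carries the on-treatment slotting of the eDiary table with it. The wording of that table, confined to eDiary records, does not support this.

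A reader might infer that days after stopping or after return necessarily count as rescue-free, or that the arm with more withdrawals is necessarily flattered. The documents support neither: the first needs a late sync and no recorded use, the second also needs unequal stopping. Nor would a gap between eMDI and eDiary results point to this rule, since the two already differ in unit (occurrences against puffs) and in model.

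**Conclusion.** The point holds in a limited form. Section 10.5.3 fixes a window for the eMDI endpoints that can admit off-treatment days, contrary to 7.3.4 with 7.1.4 and out of line with the eDiary rule. Any admitted day after final return of the inhaler is a false zero.

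The size cannot be stated from the SAP, because the frequency and length of late syncs are not given. It is nil if the last sync is on or before treatment stop. Under the assumptions above, one affected subject shifts by 4.6 to 30 percentage points, an arm mean by about 0.5 to 3.0, and the treatment difference by 0 with equal stopping or about 0.2 to 1.5 with a 5-point imbalance. The upper ends need zeros through to Day 168 and should be read as extremes. No primary or secondary conclusion depends on this rule. It still merits correction before unblinding, because it is a stated rule that contradicts the plan's own strategy.

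**What to change.** In 10.5.3, end the on-treatment eMDI observation period at the earliest of the last sync date, the study treatment stop date and Day 168. Assign zeros only to days inside that period on which the subject held an active sensor, determined for each sensor and subject as the baseline rule in 5.2 already does. Treat other days as missing.

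Do not end the period at the first collection of an inhaler. Section 10.1.1 has rescue inhalers collected and dispensed again at the clinic visits, so a cut at the routine exchanges at Visits 2–4 would discard valid on-treatment data.

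The cost is one SAP line and a date comparison in programming, with no new data.

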- [Table 2.1](#) shows examples of acceptable and unacceptable weeks after visit 1 to use in the analysis. The boxes with an 'x' indicate days with valid activity monitor data. The day of the study visit will not be used since the activity may be out of the ordinary or not meet the minimum requirement of 23 hours. For instance, if a subject had visit 1 on January 1st, 2016, the acceptable days for use would be January 2nd to January 8th (Day 2 through 8) for a total of 7 days. Data from January 9th would not be used as it is out of scope of the week-long observation criteria. Examples of selection of days for visit 2, visit 3 and visit 5 are shown in [Table 2.2](#), [Table 2.3](#) and [Table 2.4](#) respectively.

Table 2.1 Examples of Visit 1 Day Selection for Activity Monitor Analysis

Day of Activity Monitoring Target Study Day	Days With Valid Activity Monitoring Data									Use/Do Not Use
	1	2	3	4	5	6	7	8	9	
	Visit 1	Study Day -27	Study Day -26	Study Day -25	Study Day -24	Study Day -23	Study Day -22	Study Day -21	Study Day -20	
Subject ^{PP} Subject _D	x	x	x	x	x	x	x	x	x	Use Days 2-8
Subject	x			x	x	x	x			Use Days 4-8
Subject		x	x	x	x	x	x	x	x	Use Days 2-8
Subject	x	x				x		x	x	Use Days 2, 6, and 8
Subject	x	x			x					Do Not Use
Subject	x			x		x			x	Do Not Use

Table 2.2 Examples of Visit 2 Day Selection for Activity Monitor Analysis

Day of Activity Monitoring Target Study Day	Days With Valid Activity Monitoring Data									Use/Do Not Use
	1	2	3	4	5	6	7	8	9	
	Visit 2	Study Day 2	Study Day 3	Study Day 4	Study Day 5	Study Day 6	Study Day 7	Study Day 8	Study Day 9	
Subject ^{PP} Subject _D	x	x	x	x	x	x	x	x	x	Use Days 2-8
Subject	x			x	x	x	x			Use Days 4-8
Subject		x	x	x	x	x	x	x	x	Use Days 2-8
Subject	x	x				x		x	x	Use Days 2, 6, and 8
Subject	x	x			x					Do Not Use
Subject	x			x		x			x	Do Not Use

Table 2.3 Examples of Visit 3 Day Selection for Activity Monitor Analysis

Day of Activity Monitoring Target Study Day	Days With Valid Activity Monitoring Data									Use/Do Not Use
	1	2	3	4	5	6	7	8	9	
Visit 3	Study Day 29	Study Day 30	Study Day 31	Study Day 32	Study Day 33	Study Day 34	Study Day 35	Study Day 36		
Subject PP D	x	x	x	x	x	x	x	x	x	Use Days 2-8
Subject	x			x	x	x	x			Use Days 4-8
Subject		x	x	x	x	x	x	x	x	Use Days 2-8
Subject	x	x				x		x	x	Use Days 2, 6, and 8
Subject	x	x			x					Do Not Use
Subject	x			x		x			x	Do Not Use

Table 2.4 Examples of Visit 5 Day Selection for Activity Monitor Analysis

Day of Activity Monitoring Target Study Day	Days With Valid Activity Monitoring Data									Use/Do Not Use
	1	2	3	4	5	6	7	8	9	
Study Day 160	Study Day 161	Study Day 162	Study Day 163	Study Day 164	Study Day 165	Study Day 166	Study Day 167	Study Day 168	Visit 5	
Subject PP D	x	x	x	x	x	x	x	x	x	Use Days 2-8
Subject	x			x	x	x	x			Use Days 4-8
Subject		x	x	x	x	x	x	x	x	Use Days 2-8
Subject	x	x				x		x	x	Use Days 2, 6, and 8
Subject	x	x			x					Do Not Use
Subject	x			x		x			x	Do Not Use

10.5.4. Safety

Adverse Events
AE's OF Special Interest

 AE groups of special interest have been defined as AEs which have specified areas of interest for UMEC or VI or the overall COPD population. Groups which are not SMQs are made up of a selection of preferred terms (PTs) defined by GSK. The complete list, including the preferred terms which contribute to each of the groups will be provided by Global Clinical Safety and Pharmacovigilance (GCSP) using the MedDRA version at the time of reporting. This will be finalised prior to unblinding.

Special Interest AE Group	Subgroup	Sub-SMQ	SMQ Group
Anticholinergic syndrome			Anticholinergic syndrome (SMQ)
Asthma/bronchospasm			Asthma/bronchospasm (SMQ)
Paradoxical bronchospasm			
Cardiovascular effects	Cardiac Arrhythmia	Arrhythmia related investigations, signs and symptoms (SMQ)	Arrhythmia related investigations, signs and symptoms (SMQ)
Cardiovascular effects	Cardiac Arrhythmia	Bradyarrhythmia terms, nonspecific (SMQ)	Bradyarrhythmia terms, nonspecific (SMQ)
Cardiovascular effects	Cardiac Arrhythmia	Conduction defects (SMQ)	Conduction defects (SMQ)
Cardiovascular effects	Cardiac Arrhythmia	Disorders of sinus node function (SMQ)	Disorders of sinus node function (SMQ)
Cardiovascular effects	Cardiac Arrhythmia	Cardiac arrhythmia terms, nonspecific (SMQ)	Cardiac arrhythmia terms, nonspecific (SMQ)
Cardiovascular effects	Cardiac Arrhythmia	Supraventricular tachyarrhythmias (SMQ)	Supraventricular tachyarrhythmias (SMQ)
Cardiovascular effects	Cardiac Arrhythmia	Tachyarrhythmia terms,	Tachyarrhythmia terms, nonspecific (SMQ)

Special Interest AE Group	Subgroup	Sub-SMQ	SMQ Group
		nonspecific (SMQ)	
Cardiovascular effects	Cardiac Arrhythmia	Ventricular tachyarrhythmias (SMQ)	Ventricular tachyarrhythmias (SMQ)
Cardiovascular effects	Cardiac Failure		Cardiac failure (SMQ)
Cardiovascular effects	Cardiac Ischaemia		Ischaemic heart disease (SMQ)
Cardiovascular effects	Hypertension		Hypertension (SMQ)
Cardiovascular effects	Stroke		Central nervous system haemorrhages and cerebrovascular conditions (SMQ)
Pneumonia			Infective pneumonia (SMQ)
LRTI excluding infective pneumonia			
Ocular effects (antimuscarinic)			Glaucoma (SMQ)
Effects on glucose			Hyperglycaemia/new onset diabetes mellitus (SMQ)
Effects on potassium			
Gastrointestinal obstruction			Gastrointestinal obstruction (SMQ)
Hypersensitivity			
Tremor			
Urinary retention			

Exposure
Exposure Duration

• Number of days of exposure to study drug will be calculated based on the formula: Duration of Exposure in Days = Treatment Stop Date – (Treatment Start Date) + 1 
• If a subject's overall exposure stop date is missing it will be assumed to be the latest recorded exposure start or stop date in the database.• If a subject's overall exposure start date is missing then it will be assumed to be their Day 1 visit date (Visit 2).• If a subject received a treatment other than the randomized treatment during the study, the exposure will still be calculated based on overall exposure start and stop dates.• If the dose counter start=dose counter stop then it will be assumed that no doses were taken from that container.
Exposure Categories
The following exposure categories will be derived: 1-84 days, 85-168 days, >168 days

10.6. Appendix 6: Reporting Standards for Missing Data

10.6.1. Premature Withdrawals

Element	Reporting Detail
General	
 • Subject study completion (i.e. as specified in the protocol) was defined as receiving treatment at the final on-treatment clinic visit (Visit 5) and completion of the follow-up contact (Visit 6). • Withdrawn subjects will not be replaced in the study. • With the exception of the responder analyses, the minimum data required will be a baseline evaluation and at least one post-baseline evaluation. Note that this is not the case for the responder definition, see Section 10.6.2.3 for details. • All available data from subjects who were withdrawn from the study will be listed and all available planned data will be included in summary tables and figures, unless otherwise specified.

10.6.2. Handling of Missing Data

Element	Reporting Detail
General	
 • Missing data occurs when any requested data is not provided, leading to blank fields on the collection instrument: 
 ○ These data will be indicated by the use of a “blank” in subject listing displays unless all data for a specific visit are missing in which case the visit is not displayed in the listing. ○ Answers such as “Not applicable” and “Not evaluable” are not considered to be missing data and should be displayed as such. ○ No imputation will be made for any missing numerical data. Missing data will generally not be considered in the calculation of percentages (i.e., the denominator will not include subjects who have missing data at a given time point).

10.6.2.1. Handling of Missing Dates

Element	Reporting Detail
General	
 • Partial dates will be displayed as captured in subject listing displays.
Adverse Events	
 • The eCRF allows for the possibility of partial dates (i.e., only month and year) to be recorded for AE start and end dates; that is, the day of the month may be missing. In such a case, the following conventions will be applied for calculating the time to onset and the duration of the event: 
 ○ Missing Start Day: First of the month will be used unless this is before the start date of study treatment; in this case the study treatment start date will be used and hence the event is considered On-treatment as per Appendix 4: Treatment States. ○ Missing Stop Day: Last day of the month will be used, unless this is after the

Element	Reporting Detail
	
stop date of study treatment; in this case the study treatment stop date will be used.
 
 • Completely missing start or end dates will remain missing, with no imputation applied. Consequently, time to onset and duration of such events will be missing.

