10.6.2.2. Handling of Partial Dates

Element	Reporting Detail
Concomitant Medications	
 • Partial dates for any concomitant medications recorded in the CRF will be imputed using the following convention: 
 ○ If the partial date is a start date, a '01' will be used for the day and 'Jan' will be used for the month ○ If the partial date is a stop date, a '28/29/30/31' will be used for the day (dependent on the month and year) and 'Dec' will be used for the month. • The recorded partial date will be displayed in listings.
Adverse Events	
 • Any partial dates for adverse events will be raised to data management. If the full date cannot be ascertained, the following assumptions will be made: 
 ○ If the partial date is a start date, a '01' will be used for the day and 'Jan' will be used for the month. ○ However, if these results in a date prior to Week 1 Day 1 and the event could possibly have occurred during treatment from the partial information, then the Week 1 Day 1 date will be assumed to be the start date. ○ The AE will then be considered to start on-treatment (worst case). ○ If the partial date is a stop date, a '28/29/30/31' will be used for the day (dependent on the month and year) and 'Dec' will be used for the month. • The recorded partial date will be displayed in listings.

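### The two adverse event date rules conflict: Section 10.6.2.1 makes an onset in a month that ended before dosing on-treatment, where Section 10.6.2.2 leaves it pre-treatment

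*SAP*

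**What the plan says.** Section 10.6.2.1 (Handling of Missing Dates, Adverse Events) deals with AE dates for which only month and year were recorded. For the start it says "First of the month will be used unless this is before the start date of study treatment"; when it is before, "in this case the study treatment start date will be used and hence the event is considered On-treatment as per Appendix 4: Treatment States". For the stop it takes the last day of the month unless that falls after treatment stop: "in this case the study treatment stop date will be used". A further bullet leaves completely missing dates missing.

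Section 10.6.2.2 (Handling of Partial Dates, Adverse Events) covers any partial AE date. Such dates are first raised with data management, and imputation follows only if the full date cannot be found. A partial start takes the first as its day and January as its month. If that precedes Day 1, it is moved only where "the event could possibly have occurred during treatment from the partial information, then the Week 1 Day 1 date will be assumed". For the stop, "If the partial date is a stop date, a '28/29/30/31' will be used for the day" and December is the month, with no reference to treatment stop.

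Section 10.3.2 defines on-treatment as treatment start through treatment stop plus one day.

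**The concern.** Both sections apply to an AE recorded with month and year only, and nothing ranks one above the other. Section 10.6.2.1 has no overlap test, so it replaces a month known to lie wholly before treatment with the first day of treatment. That overrides recorded information; it does not resolve an uncertain date conservatively. Two programmers who each follow the SAP can therefore assign different phases to the same event.

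Phase decides which display an event enters. Incidence of adverse events is the only safety endpoint in Section 2.2, and most tables in Section 10.8.6 are restricted to on-treatment events, including those for drug-related events, serious events and events of special interest. Pre-treatment serious events have their own display (Table 3.06), which would lose whatever is moved.

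The stop-date cap is a smaller matter. It can date the end of a post-treatment event before its beginning, but phase depends on onset, so it does not change which table counts the event.

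**Working it through.** The SAP gives no figure to reproduce, so I applied both sets of rules to example dates.

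**Assumed inputs.** Treatment start 15 September 2017 and stop 1 March 2018, which is 168 days. By Section 10.3.2 the on-treatment phase then runs to 2 March 2018. Duration is taken as stop − start + 1; the SAP states that formula for exacerbations, and using it for AEs is my assumption.

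**Start day missing.** In the last column January is used only when the month is missing.

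| Recorded onset | 10.6.2.1 | 10.6.2.2 |
|---|---|---|
| July 2017 | 15 Sep 2017, on-treatment | 1 Jul 2017, pre-treatment |
| August 2017 | 15 Sep 2017, on-treatment | 1 Aug 2017, pre-treatment |
| September 2017 | 15 Sep 2017, on-treatment | 15 Sep 2017, on-treatment |
| October 2017 | 1 Oct 2017, on-treatment | 1 Oct 2017, on-treatment |

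The sections disagree exactly where the recorded month ended before dosing. If January is read literally, as replacing a known month, July and August become 1 January 2017 and are still pre-treatment. The October onset then goes to 15 September 2017: the phase is the same but the onset date is wrong. The January wording therefore also needs tidying.

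**Inverted dates from the start rule in 10.6.2.1.**
- Onset August 2017, known stop 20 August: start 15 September, stop 20 August, duration −26 + 1 = −25 days.
- Onset and stop both August 2017, days missing: start 15 September, stop 31 August, duration −15 + 1 = −14 days.

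**Inverted dates from the stop cap.** Known start 5 March 2018, stop recorded as March 2018: 10.6.2.1 gives a stop of 1 March and a duration of −4 + 1 = −3 days. Section 10.6.2.2 gives 31 March 2018.

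**Same-month case, which any fix must handle.** Onset September 2017, known stop 10 September 2017: 10.6.2.1 gives a start of 15 September, on-treatment, five days after the event ended. Moving the date whenever month and year match those of dosing would give the same wrong answer. The known stop date has to be used as well.

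**The case against.** One defence is that the sections serve different purposes, since 10.6.2.1 introduces its rules with "the following conventions will be applied for calculating the time to onset and the duration of the event". This does not remove the conflict, because the same bullet goes on to declare the event on-treatment.

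A second defence is that moving events into the on-treatment phase is conservative, and 10.6.2.2 does describe its own shift as worst case. That justifies the shift when timing is uncertain. It does not when the recorded month already rules out treatment.

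Other points stand and limit the weight. Partial dates are queried before imputation under 10.6.2.2, so few may remain. The rule is identical in three randomised, double-blind arms. No table or figure listed in Sections 10.8.6 and 10.8.7 is titled for AE duration or time to onset, and partial dates are listed as captured, so negative durations reach no display named there.

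A reader might go further and infer that a large share of early AEs is misclassified. If onsets were uniform over a 28-day or 70-day pre-treatment period, about 48% or 79% would fall in a calendar month before the dosing month. The documents do not support those figures as an effect size. The schedule marks AEs from pre-screening, but its footnote 6 refers the start of collection to an appendix whose text is not in this SAP. The 70-day case needs the full optional pre-screening period, uniform onset is an assumption, and the base is only pre-treatment AEs with an unresolved missing day, whose number is unknown.

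**Conclusion.** The start rule in 10.6.2.1 is wrong as written and conflicts with 10.6.2.2. An AE whose recorded month ended before dosing is on-treatment under one section and pre-treatment under the other. This follows from the text and needs no assumption about frequency. The stop-date cap is a genuine but secondary defect.

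The main effect is some inflation of on-treatment AE counts. Its size cannot be calculated, because the number of unresolved partial dates is not given; it is probably small. A reader might infer a bias between treatments, but the rule applies equally to every arm and nothing in the document shows a systematic difference. Nor does the rule touch the primary efficacy analysis. The case for correcting it is that the plan should give one reproducible phase for each event and that the correction is cheap.

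**What to change.** 1. In Section 10.6.2.1, remove the Missing Start Day and Missing Stop Day bullets. Keep the bullet under which completely missing dates stay missing. The reference to Appendix 4 for treatment states goes with the removed text; the study phases are in Appendix 3.
2. Let Section 10.6.2.2 govern all partial AE dates, and state in it that:
   - January and December are imputed only when the month itself is missing;
   - the start moves to treatment start only if the recorded month and year, together with any known stop date, allow onset on or after treatment start;
   - an imputed stop date is the last day of the month, never earlier than the AE start date and not capped at treatment stop.

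On the examples above, July and August onsets stay pre-treatment. A September onset goes to 15 September unless its known stop date is earlier, in which case it stays at 1 September, pre-treatment. The post-treatment event ends on 31 March 2018.

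The cost is SAP wording and a small programming change.
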